11.0 STATISTICAL METHODS

This is a pilot study with the intention of gathering data to assess feasibility and imaging metrics. Therefore, no formal statistical hypothesis testing will be performed for making development decisions. Considerations for outcome assessment are described in Appendix 3.

11.1 Data Management

All data generated by the sites for this study will be entered by the Investigator (or designee) onto a validated eCRF provided for this study by the Contract Research Organization (CRO). Study Data Tabulation Model datasets will be prepared from the eCRF data by the CRO using validated software. Details will be provided in the study's Data Management Plan and Statistical Analysis Plan (or equivalents).

11.2 Analysis Populations

The analysis populations that will be used in the statistical analysis are defined below:

A patient is considered to have completed the study if the patient has completed all phases of the study, including the last visit or the last scheduled procedure (Figure 1,

Table 3,

Table 4/4A, and Table).

11.3 Study Population and Patient Characteristics

The study population and patient characteristics will be analyzed in the Safety population.

Demographics (including age, gender, race, ethnicity, and BMI), medical history (prior therapies with dates, histology, localization and classification of cancer, prior treatment outcome), and administration of study drug will be summarized using descriptive statistics.

Surgical care (including type, duration, and outcome) and tumor characteristics (including morphology, size, and margin status) will be summarized using descriptive statistics.
11.4 Efficacy Analyses

This is a pilot study with the intention of gathering data to assess feasibility and imaging metrics for the efficacy analysis. Therefore, no formal statistical hypothesis testing will be performed for making development decisions. Considerations for outcome assessment are described in Appendix 3.

Imaging and diagnostic performance analyses will be analyzed using graphical methods and descriptive statistics.

11.5 Safety Analyses

The safety analyses will be assessed in the Safety Population.

Adverse events, vital signs, ECGs, and conventional clinical laboratory data (CMP and CBC with differentials) will be summarized using descriptive statistics.

Adverse events will be coded using the Medical Dictionary for Regulatory Activities (MedDRA) Version 21.1. The incidence of TEAEs will be presented by system organ class and preferred term, by relationship to study drug, by severity, and by whether or not they resulted in alteration of administration of or discontinuation of study drug. A TEAE is defined as an AE that occurs during or after study drug administration and up through 28 days (±48 hours) in Part 1 or 28 days (±5 days) in Part 2 after administration of study drug. In addition, the incidence of SAEs and TEAEs leading to discontinuation of study drug will be presented by system organ class, preferred term, and relationship to study drug.

Descriptive statistics for clinical laboratory test results and vital signs, and for changes from Baseline, will be presented by time point. Baseline is defined as the measurement closest to, but before, the administration of study drug. Incidences of potentially clinically meaningful clinical laboratory results and vital signs, determined based on normal ranges and percentage changes from Baseline, will also be summarized by time point. The number and percentage of abnormal ECGs will be provided by time point.

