The Sponsor will inform Investigators when each Group has been opened to enrollment and provide the dose and, as applicable, dose schedule to be used in each Group, and when any tumor type is activated or deactivated for enrollment. Any Group in Part 2 may begin dosing at any time during Part 1 if the safety and observed detection of metastatic lymph nodes or the primary tumors at the same or higher dose level has been demonstrated in Part 1.

Schematics of the study designs for Part 1 and Part 2 are presented in Figure 1. The Schedule of Assessments and Procedures for Part 1 (all cohorts) (

Table 3), Part 2 for Groups dosing on Day of surgery (Table 4), and Part 2 for Groups dosing ≥ 1 days (16-80 hours) before surgery (Table 4A) are presented. Note that the timing provided for postdose assessments and procedures begins after infusion of study drug has been completed (ie, time = 0 begins at the end of study drug infusion).

On Day 0, each patient will receive a single IV dose of ONM-100. The ONM-100 dose level, surgery time, and imaging schedule will be based on the Cohort in Part 1 or Group in Part 2 in which each patient is enrolled. The patient will undergo anesthesia in accordance with standard surgical practice. The surgery with tissue excision will occur as per routine surgical standards and the surgical specimens will be collected for pathologic evaluations.

imaging results will be used for any therapeutic or patient management decisions intraoperatively or post operatively.

After surgery, the patient will be strictly observed following the standard, respective, postoperative protocol. Patients will be monitored for safety assessments and PK sample procurement.

Medical history, prior medication use, hemoglobin, and Karnofsky performance status will be evaluated at Screening and pretreatment on Day 0. Pregnancy tests will be performed at Screening and at Day 28 (\pm 48 hours) in Part 1 and at Day 28 (\pm 5 days) in Part 2. Electrocardiograms (ECGs) will be performed pretreatment and at 30 \pm 10 minutes postdose on Day 0.

Plasma samples for PK analyses will be collected from all patients pretreatment and at various time points up to Day 6 (± 24 hours) in Part 1 and up to Day 1 (± 8 hours) in Part 2.

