The Schedule of Assessments and Procedures for Part 3 are presented in Table 5. Note that the timing provided for postdose assessments and procedures begins after infusion of study drug has been completed (ie, time = 0 begins at the end of study drug infusion).

On Day 0, each patient will receive a single IV dose of ONM-100. The patient will undergo anesthesia in accordance with standard surgical practice.

All the ONM-100 fluorescence images will be saved per the Imaging Manual.

After surgery, the patient will be strictly observed following the standard, respective, postoperative protocol. Patients will be monitored for safety assessments.

Medical history, prior medication use, hemoglobin, and Karnofsky performance status will be evaluated at Screening and pretreatment on Day 0. Pregnancy tests will be performed at Screening and

Protocol Amendment 6.0

at Day 28 (\pm 5 days). Electrocardiograms (ECGs) will be performed pretreatment, at 30 \pm 10 minutes postdose on Day 0, and on Day 10 (\pm 5 days).

Patient safety will be assessed for 28 days (\pm 5 days). All patients will be monitored for vital signs and physical examination pretreatment and at various time points up to Day 10 (\pm 5 days). All patients will be monitored for comprehensive metabolic panel (CMP) and complete blood count (CBC) with differentials pretreatment and at various time points up to Day 28 (\pm 5 days). All patients will be monitored for TEAEs and concomitant medication use from the start of dosing up to Day 28 (\pm 5 days). TEAEs will be followed closely during the study.

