9.1.3.1 Predose procedures

- Clinical assessments
 - Record weight and height, calculate BMI
 - o Record medical signs and/or symptoms since Screening visit
 - Measure vital signs (temperature, heart rate, blood pressure, and respiratory rate)
 - Perform 12-lead ECG during pre-operative screening anesthesia
 - Determine Karnofsky Performance Status (Appendix 1)
 - o Install an IV line
- Laboratory assessments

 - Perform test for alcohol only for patients who have a known medical history of alcohol abuse; serum or urine test for alcohol is acceptable. If urine test is used and tests positive, a confirmatory serum test may be used to rule out false positive results.
 - Obtain predose blood sample for PK analyses and blood volume (Part 1 & 2 Only)
- · Record all prior medications since Screening visit
- Confirm that the patient meets all study inclusion and exclusion criteria

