9.1.6 Day 3 (±24 hours) (Part 1 only)

• Laboratory assessments

- Obtain blood sample for PK analyses and blood volume (Part 1 & 2 Only)
 - Part 1 (all cohorts): 72 (±24) hours postdose (ie, after infusion has been completed)
- Record all concomitant medications including prescription, OTC, and herbal medications
- Assess, identify, and record any new TEAEs

9.1.7 Day 6 (±24 hours) in Part 1 ;and Day 10 (±5 days) in Part 2 and Part 3

- Clinical assessments
 - Measure vital signs (temperature, heart rate, blood pressure, and respiratory rate)
 - Perform 12-lead ECG
 - Conduct complete physical examination
- Laboratory assessments

• Obtain blood sample for PK analyses and blood volume (Parts 1 & 2)

- Record all concomitant medications including prescription, OTC, and herbal medications
- Assess, identify, and record any new TEAEs

9.1.8 Day 28 (±48 hours) in Part 1; Day 28 (±5 days) in Part 2 and Part 3

Laboratory assessments

- Perform serum pregnancy test on female patients <2 years postmenopausal
- Record all concomitant medications including prescription, OTC, and herbal medications
- Assess, identify, and record any AEs

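### The ECG summary fixed in section 11.5 gives the net change in abnormal ECGs but usually not the number of patients who became newly abnormal after dosing (minor)

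*Protocol*

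**What the plan says.** Protocol section 11.5 first makes a general statement: "Adverse events, vital signs, ECGs, and conventional clinical laboratory data (CMP and CBC with differentials) will be summarized using descriptive statistics". It then becomes specific by type of data. For laboratory tests and vital signs: "Descriptive statistics for clinical laboratory test results and vital signs, and for changes from Baseline, will be presented by time point". Baseline is defined next: "Baseline is defined as the measurement closest to, but before, the administration of study drug". For ECGs the specific sentence is "The number and percentage of abnormal ECGs will be provided by time point". The synopsis uses the same wording for the ECG summary.

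A pretreatment ECG is planned in all three parts. Section 6.1 says for Parts 1 and 2 that "Electrocardiograms (ECGs) will be performed pretreatment and at 30" ± 10 minutes after dosing on Day 0, and lists no later ECG. For Part 3 it says "Electrocardiograms (ECGs) will be performed pretreatment, at 30" ± 10 minutes after dosing, and adds Day 10. The schedules for Parts 1 and 2 go further than the section 6.1 text: Table 3 marks an ECG at Day 6 and Tables 4 and 4A mark one at Day 10. Section 9.1.7, which covers Day 6 in Part 1 and Day 10 in Parts 2 and 3, also lists "Perform 12-lead ECG".

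Section 10.5.4.1 requires an abnormal ECG to be recorded as a TEAE or SAE when it comes with signs or symptoms. Section 11.1 refers to a statistical analysis plan for details.

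**The concern.** The plan sets Baseline-referenced summaries for two kinds of safety data and a plain count for the third, in the same paragraph and with paired ECGs available for every patient. The useful question for an infused agent is how many patients with a normal ECG before dosing had an abnormal one afterwards. A count at each time point answers a different question, namely how many were abnormal at that moment. Patients whose abnormality resolved offset patients whose abnormality is new, so equal counts before and after dosing do not establish that nothing happened.

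The adverse event tables do not fully cover the gap. A new ECG abnormality without signs or symptoms need not become a TEAE under section 10.5.4.1, and section 10.5.6 defines dose-limiting toxicity from TEAEs. For such an abnormality, the count by time point is the only ECG-specific summary that the protocol names.

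The section 6.1 omission is a separate matter of consistency. It affects which ECGs a site believes it must perform in Parts 1 and 2.

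**Working it through.** The protocol gives no ECG figure to reproduce, so the check is what a table of counts by time point can and cannot determine.

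**Inputs.** Patient numbers come from section 6.2 and the synopsis: up to 15 in Part 1 (cohorts of 3), about 10 to 20 in Part 2, about 20 to 30 in Part 3. The protocol gives no rate of abnormal ECGs, so every rate below is an assumption, shown over a range.

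**Formula.** Let N be the number of patients with both ECGs, *a* the number abnormal before dosing, *b* the number abnormal after dosing, *r* the number that resolved and *n* the number newly abnormal. Then

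b = a − r + n, so n = (b − a) + r.

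The table gives *a* and *b* but not *r*. Since r lies between 0 and a, and n cannot exceed the N − a patients who started normal,

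max(0, b − a) ≤ n ≤ min(b, N − a).

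**Results.**

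| N | Abnormal before | Abnormal after | Lower bound | Upper bound | Newly abnormal |
|---|---|---|---|---|---|
| 30 | 3 (10%) | 3 | max(0, 0) = 0 | min(3, 27) = 3 | 0-3 |
| 30 | 6 (20%) | 6 | max(0, 0) = 0 | min(6, 24) = 6 | 0-6 |
| 30 | 12 (40%) | 12 | max(0, 0) = 0 | min(12, 18) = 12 | 0-12 |
| 30 | 6 (20%) | 8 | max(0, 2) = 2 | min(8, 24) = 8 | 2-8 |
| 15 | 3 (20%) | 3 | max(0, 0) = 0 | min(3, 12) = 3 | 0-3 |
| 3 | 1 | 1 | max(0, 0) = 0 | min(1, 2) = 1 | 0-1 |
| 30 | 0 | 2 | max(0, 2) = 2 | min(2, 30) = 2 | exactly 2 |

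As a share of those normal before dosing, the first three upper bounds are 3/27 = 11%, 6/24 = 25% and 12/18 = 67%.

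The table by time point therefore always shows the net change b − a, and a net rise is a lower bound on new abnormalities. It gives the exact number only in special cases, chiefly when nobody is abnormal before dosing. The upper bounds are logical limits: in the equal-count rows they require every pre-existing abnormality to resolve by the later ECG. They are not predictions.

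**ECG schedule in Parts 1 and 2, side by side.**

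| Place | Pretreatment | 30 ± 10 min | Later ECG |
|---|---|---|---|
| Section 6.1 text, Parts 1 and 2 | yes | yes | none listed |
| Table 3 (Part 1) | yes | yes (dosing column; time from section 9.1.3.2) | Day 6 |
| Tables 4 and 4A (Part 2) | yes | yes (dosing column; time from section 9.1.3.2) | Day 10 |
| Section 9.1.7 | – | – | Day 6 (Part 1), Day 10 (Part 2) |

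The text of section 6.1 disagrees with the other three on the later ECG.

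**The case against.** The strongest reply is that a shift table is ordinary analysis-plan content. The protocol defers details to a statistical analysis plan that is not shown, and adding the table would contradict nothing. That largely stands, and it is why the point is minor. What remains is that the protocol is not silent here: it chose a specific form for ECGs and placed it beside Baseline comparisons for the other data.

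Several stronger readings are tempting, and the document does not support them.

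- A reader might infer that the count by time point is the only ECG output. Section 11.5 does not say so; it also promises unspecified descriptive statistics for ECGs and excludes nothing.
- A reader might infer that the table cannot show an effect of dosing, or that a high background rate could pass for one. Pretreatment is one of the tabulated time points, so a net rise is visible and the background rate appears in the table before any dose.
- A reader might infer that new ECG findings would go unseen altogether. Those with signs or symptoms enter the TEAE tables, and section 10.5.6 has the safety results of each Part 1 cohort reviewed by an internal committee.
- A reader might infer a timing conflict from section 9.1.3.1, which says "Perform 12-lead ECG during pre-operative screening anesthesia". The wording is awkward, but the line stands among the predose procedures under the Day 0 dosing heading, which agrees with the tables. The table footnotes on ECGs are not in the available copy, so nothing further can be concluded.
- A reader might infer that a Baseline rule for ECGs is missing. The definition in section 11.5 is general and can be applied to them.

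It is also fair to say that the size rests on assumed rates and that the ambiguity is small if few ECGs are abnormal before dosing.

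**Conclusion.** The point holds as a minor weakness in reporting. The ECG summary specified in section 11.5 and the synopsis shows net change but, unless special conditions hold, leaves the number of newly abnormal patients as a range. For 30 patients with unchanged counts, that range is 0-3 at an assumed 10% abnormal, 0-6 at 20% and 0-12 at 40%; it closes to a single value when none are abnormal before dosing. The conclusion assumes that some patients have an abnormal pretreatment ECG and that some new abnormalities come without signs or symptoms. The protocol quantifies neither. No stated figure is wrong, and the data needed for the better summary are already collected.

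The omission in section 6.1 is a genuine internal inconsistency. It does not bear on the choice of summary.

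**What to change.** In section 11.5 and the synopsis, keep the count by time point and add a within-patient shift table (normal or abnormal) from Baseline, as section 11.5 already defines it, to 30 minutes and to the Day 6 or Day 10 ECG. Report the number and percentage newly abnormal among patients normal at Baseline. The cost is one additional table, with no new procedure.

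Separately, reconcile the ECG schedule for Parts 1 and 2 in section 6.1 with Tables 3, 4 and 4A and section 9.1.7, so that all of them list the same ECGs. This is a text correction; if it changes which later ECG is performed, the shift table should follow.

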11.6 Pharmacokinetic Analyses

The PK analyses will be assessed in the Pharmacokinetic Population.

Plasma concentration-time profiles will be constructed for each patient and each dosing cohort. Plasma concentration values will be summarized at each time point using mean, standard deviation, median, and range.

Summary PK parameters will be summarized using mean, standard deviation, median, and range.

11.7 Determination of Study Sample Size

11.8 Handling of Dropouts and Missing, Unused, and Spurious Data

All data will be analyzed. Data identified as spurious will be treated as missing unless they can be definitively corrected.

The incidence of missing data is expected to be quite low due to the structure of the trial. Therefore, complete case analysis will be performed. Sensitivity analysis will be performed to assess the potential impact of any missing data on trial results.

11.9 Termination Criteria

Enrollment and withdrawals from the study and from study drug will be summarized.

11.10 Deviation Reporting

Protocol deviations will be summarized. Protocol deviations are defined as any variation from the protocol, including enrollment of a patient who did not meet all inclusion and exclusion criteria and failure to perform the assessments and procedures within the required time frame.

12.0 INVESTIGATOR REQUIREMENTS

12.1 Protocol Adherence

The Investigator must adhere to the protocol as detailed in this document and agree that the Sponsor must approve any change to the protocol before seeking approval from the IRB/IEC. The Investigator will be responsible for enrolling only those patients who have met the protocol inclusion and exclusion criteria.

12.2 Electronic Case Report Forms

The eCRF will be supplied by the contract research organization or designee for the recording of all information and study data as specified by this protocol. All eCRFs must be completed by trained study personnel. The Investigator is responsible for ensuring that the eCRF data are entered and completed in a timely manner.

Once all data queries and issues have been resolved for each patient, the Investigator will electronically sign each patient's eCRF to attest to the accuracy of the data.

12.3 Source Document Maintenance

Source documents are defined as documentation related to original observations and activities of a clinical investigation. Source documents may include, but are not limited to, study progress notes, study- or patient-specific e-mail correspondence, computer printouts, clinical laboratory data, and recorded data from automated instruments. All source documents produced in this study will be maintained by the Investigator and made available for inspections by the Sponsor and by regulatory authorities. The original signed ICF for each participating patient shall be filed with records kept by the Investigator, and a signed and dated copy will be given to the patient. In all cases, subject confidentiality must be maintained in accordance with local regulatory requirements.

12.4 Study Monitoring Requirements

An authorized Sponsor representative will conduct site visits to inspect study data, patients' medical records, and eCRFs in accordance with ICH guidelines, GCPs, and the foreign regulations and guidelines, as applicable. A monitor will be utilized for monitoring ongoing drug accountability and adherence to protocol procedures.

The Investigator will allow representatives of the Sponsor and regulatory authorities to inspect facilities and records relevant to this study.

12.5 Study Completion

The Sponsor requires the following data and materials before a study can be considered complete or terminated:

- Laboratory findings, clinical data, and all special test results from Screening throughout the study until the Follow-up visit
- eCRFs (including data queries) properly completed by appropriate study personnel and signed and dated by the Investigator
- Copies of complete drug accountability records (drug inventory log and an inventory of returned or destroyed clinical material)
- Copies of protocol amendments and IRB/IEC approval and notification, if appropriate
- A summary of the study prepared by the Investigator (an IRB/IEC summary letter is acceptable)

13.0 QUALITY CONTROL AND QUALITY ASSURANCE

Written standard operating procedures (SOPs) will be followed to ensure that the study is conducted and data are generated, documented (recorded), and reported in compliance with the protocol, GCP, and the applicable regulatory requirements. Quality control will be applied to each stage of data handling. Regular monitoring, as defined in ICH GCP, Section 1.8, "The act of overseeing the progress of a clinical trial, and of ensuring that it is conducted, recorded, and reported in accordance with the protocol, SOPs, GCP, and the applicable regulatory requirement(s)", will be conducted throughout the conduct of the study.

The purpose of monitoring is to verify that:

- Rights and well-being of the human patients are protected
- The reported study data are accurate, complete, and verifiable from source documents
- The conduct of the study is in compliance with the currently approved protocol/amendment(s), with GCP, and with the applicable regulatory requirements
- Monitoring is an integral role in the quality control of a clinical trial and is designed to verify the quality of the study

To fulfill the Quality Assurance requirements of GCP, audits will be conducted to assess and assure the reliability and integrity of a study's quality control systems and recognized standards.

The purpose of an audit is to:

- Ensure participant safety
- Assure compliance to study protocol procedures, regulatory requirements, and SOPs
- Assure data quality

Protocol Amendment 6.0

14.0 PROTECTION OF HUMAN SUBJECTS

This study will be conducted in compliance with the ICH Technical Requirements for Registration of Pharmaceuticals for Human Use including ICH E6 GCP (2016), the ethical principles of the Declaration of Helsinki (2013), US FDA Code of Federal Regulations Title 21 Food and Drugs (2018), and any additional national or IRB/IEC-required procedures.

